#### **6.6.5. Electrocardiogram**

Triplicate ECGs assessments are required at each specified nominal visit and time-point as specified in the Schedule of Activities in the Protocol (Table 2 for Intensive and Table 4 for Non-intensive). A mean value is calculated for any replicate measurements having the same nominal visit. The mean measurement is reported.

QTcF and QTcB (both Fridericia and Bazett's correction) will be programmatically derived using the following formula:

$$QTcF(\text{msec}) = QT(\text{msec}) / (60 / \text{HR}[\text{bpm}])^{1/3}$$

$$QTcB(\text{msec}) = QT(\text{msec}) / (60 / \text{HR}[\text{bpm}])^{1/2}$$

QT, RR, HR, PR, QRS, QTcF, and QTcB will be summarized using simple descriptive statistics (mean, standard deviation, median, quartiles, minimum, and maximum) of actual values and change from baseline for each nominal visit over time (ie, unscheduled assessments will be excluded). The total number of patients for change from baseline will include all patients in the treatment arm who have both a baseline and a value at the nominal visit. Baseline will be selected as defined in [Section 3.4](#).

The mean absolute value will be presented with two-sided 95% confidence intervals and the baseline adjusted mean QT, RR, HR, PR, QRS, QTcF and QTcB will be presented with two-sided 90% confidence intervals.

Additionally QTcF and QTcB will be summarized by maximum post-baseline values using the following categories.

- $\leq 450$  msec;
- $>450$  msec but  $\leq 480$  msec;
- $>480$  msec but  $\leq 500$  msec;
- $>500$  msec.

Unscheduled assessments will be utilized in addition to planned assessments.

And maximum increases from baseline in QTcF and QTcB (including scheduled and unscheduled assessments) will be also summarized based on the following categories:

- Change  $\geq 60$  msec;
- Change  $\geq 30$  msec but  $<60$  msec;
- Change  $<30$  msec.

In the event that neither Fridericia's nor Bazett's correction adequately adjusts for heart rate, an additional correction such as a population or patient-specific baseline correction could be used and should be fully justified.

For PR and QRS maximum increases from baseline, the following categories will be applied:

- PR changes from baseline  $\geq 25\%$  and absolute values  $>200$  msec;
- QRS changes from baseline  $\geq 25\%$  and absolute values  $>110$  msec.

Shift tables will be provided for baseline versus worst on study QTc (one or more correction method will be used) using categories  $\leq 450$  msec,  $>450$  msec but  $\leq 480$  msec,  $>480$  msec but  $\leq 500$  msec, and  $>500$  msec. Tables of ECG abnormality at baseline (yes, no, not done: (n, %)) will also be provided. Subjects experiencing abnormal and clinically-relevant morphological ECG changes will be summarized (including frequency and percentage).

If more than one ECG is measured at a nominal time post-dose (eg, triplicate ECGs within 2-4 minutes), the mean will be used to represent a single observation per patient and time post-dose. If any of the three individual ECGs results in a QTc >500 msec and the mean is not >500 msec, then that patient's data will be described in the safety section in the study report in order to place the >500 msec value in appropriate clinical context. On the other hand, such individual >500 msec value within a triplicate will not be included in the categorical analysis unless the average from that triplicate is also >500 msec. Data listings will contain the means from a triplicate as well as the parameters from each of the three ECGs. Note that using the mean value may result in a patient having a measurement that is not represented by an actual ECG.

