#### Secondary Objectives:

- To compare fatigue score post baseline as measured by MDASI AML/MDS in both treatment arms;
- To compare glasdegib versus placebo in combination with azacitidine (non-intensive study) or '7+3' (cytarabine and daunorubicin) in improving other clinical efficacy measures;
- To estimate the duration of response in both treatment arms;
- To estimate the time to response in both treatment arms in the Non-intensive study only;
- To compare Event-free Survival (EFS) in both treatment arms;
- To compare PRO measurements in both treatment arms;
- To evaluate the overall safety profile in both treatment arms;
- To evaluate laboratory abnormalities in both treatment arms;

- To characterize the PK of glasdegib;
- To characterize treatment effects on the QTc interval.

CCI

[figure not shown]

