## 2.2. Study Design

Two separate registration trials conducted under one protocol number are proposed to adequately and independently evaluate the addition of glasdegib in intensive and non-intensive chemotherapy populations. Each study will have an experimental treatment arm and a placebo arm.

Study B1371019 (Figure 1) is a randomized (1:1), double-blind, multi-center, placebo controlled study of chemotherapy in combination with glasdegib versus chemotherapy in combination with placebo in adult patients with previously untreated AML (excluding APL with PML-RARA, AML with BCR-ABL1 and active central nervous system [CNS] leukemia) to support the proposed indication statements:

- Intensive Study: Glasdegib is being studied in combination with cytarabine and daunorubicin for the treatment of adult patients with untreated AML.
- Non-intensive Study: Glasdegib is being studied in combination with azacitidine for the treatment of adult patients with untreated AML who are not candidates for intensive induction chemotherapy.

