## 5.2. General Methods

Unless otherwise specified, baseline data will be summarized by treatment arm and for both treatment arms combined. Disposition, efficacy, exposure (including concomitant therapies), and safety data will be summarized by treatment arm only. The intensive and non-intensive chemotherapy patients will be analyzed separately.

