### 6.3.4. Population Pharmacokinetic Analysis or PK/PDx Modeling

PK and pharmacodynamics (PDx) data from this study may be analyzed using modeling approaches and may also be pooled with data from other studies to investigate any causal relationship between study treatment exposure and biomarkers or significant safety endpoints. The results of these analyses, if performed, may be reported separately.

CCI [REDACTED]

[REDACTED]

[REDACTED]

- | [REDACTED]
- | [REDACTED]
- | [REDACTED]
- | [REDACTED]
- | [REDACTED]
- | [REDACTED]
- | [REDACTED]
- | [REDACTED]
- | [REDACTED]
- | [REDACTED]
- | [REDACTED]
- | [REDACTED]
- | [REDACTED]
- | [REDACTED]
- | [REDACTED]
- | [REDACTED]

[REDACTED]

CCI

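### QTc: the readable ECG plan gives per-arm summaries but no glasdegib-minus-placebo estimate or interval for a secondary objective about treatment effects

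*SAP*

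**What the plan says.** Both documents list the same secondary objective: "To characterize treatment effects on the QTc interval" (protocol section 2; SAP 2.1). SAP 2.2 describes the design as a "randomized (1:1), double-blind, multi-center, placebo controlled study of chemotherapy" with glasdegib or placebo. Protocol Tables 2 and 4 each set one triplicate-ECG schedule for both arms, timed to the glasdegib/placebo dose.

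The analysis text is organised by arm:

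- SAP 5.2, on safety data in general: "and safety data will be summarized by treatment arm only".
- SAP 6.6.5, on the population for change from baseline, visit by visit: "The total number of patients for change from baseline will include all patients in the treatment arm who have both a baseline and a value".
- SAP 6.6.5, on intervals: absolute means get 95% intervals, whereas for the baseline-adjusted means the statement is that "QTcF and QTcB will be presented with two-sided 90% confidence intervals". The term baseline-adjusted mean is not defined.
- SAP 6.6.5 also plans categories of maximum value and maximum increase, and shift tables.
- Protocol 9.5.4.1 plans descriptive statistics (n, mean, median, SD, minimum, maximum) by treatment and time point, with similar outlier categories. Protocol 9.5.4 makes QTcF the primary correction.
- SAP 6.3.4 leaves exposure modelling optional and does not mention QTc: "PK and pharmacodynamics (PDx) data from this study may be analyzed using modeling approaches".

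**The concern.** In a randomised placebo-controlled trial, the treatment effect on QTc is the difference between arms. The readable ECG sections contain no such difference, no model with a treatment term and no interval for a contrast.

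This matters because QTc may move in both arms for reasons unrelated to glasdegib. All patients receive chemotherapy. Protocol 5.8.1 discourages drugs with a known Torsade risk but does not bar them, and Appendix 8 lists ondansetron, fluconazole and levofloxacin among them. Any common drift enters each arm's change from baseline, and so enters the glasdegib 90% interval. If the report relies on that interval, drift can be taken for drug effect, or a drug effect can be masked by a fall in the background. The placebo arm was designed to remove this, but the subtraction is not in the readable plan.

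**Working it through.** The documents give no sample size, margin or precision for QTc, so there is no planned figure to reproduce. The check is a comparison of the texts, followed by the precision that the missing contrast would have.

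**1. Is the silence shorthand?** It does not appear to be. For MDASI-AML/MDS and EQ-5D-5L, SAP 6.2.6.1 and 6.2.6.2 plan the same by-arm descriptive tables and then add a comparison of the two groups by a repeated-measures mixed model with baseline as covariate. SAP 6.6.5 has no such sentence.

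**2. What the per-arm interval estimates.** Let the drug effect be d and the common drift b. The mean change estimates d + b under glasdegib and b under placebo. The glasdegib interval is therefore centred on d + b, while the difference is centred on d.

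**3. Precision.** Inputs:

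- 400 and 320 subjects (SAP 5.1.1) at 1:1, so 200 and 160 per arm.
- SD of QTcF change of 15–25 msec (assumed).
- Share of subjects with an ECG at the time point of 70–100% (assumed), with 50% as a stress case.

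Normal-approximation 90% half-widths:

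- within one arm: 1.645 × SD / √n
- difference: 1.645 × SD × √(2/n)

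Example: 1.645 × 15 × √(2/200) = 1.645 × 15 × 0.1 = 2.5 msec.

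| Study | n per arm (share) | SD | Within arm | Difference |
|---|---|---|---|---|
| Intensive | 200 (100%) | 15 | 1.7 | 2.5 |
| Intensive | 140 (70%) | 25 | 3.5 | 4.9 |
| Intensive | 100 (50%) | 25 | 4.1 | 5.8 |
| Non-intensive | 160 (100%) | 15 | 2.0 | 2.8 |
| Non-intensive | 112 (70%) | 25 | 3.9 | 5.5 |
| Non-intensive | 80 (50%) | 25 | 4.6 | 6.5 |

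With equal n and SD, the within-arm interval is narrower than the interval for the difference by a factor of √2. Comparing the ends of the two per-arm intervals does not give a 90% interval either. It spans ±2 × 1.645 × SD/√n, which is 1.645 × √2 = 2.33 standard errors of the difference, or about 98% confidence.

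**4. Where randomisation protects the comparison.** Drift cancels reliably only while the randomised groups are nearly complete. That covers Induction 1 Day 1 and Day 10 in the intensive study, and Cycle 1 Day 1 and Day 15 in the non-intensive study, all with ECGs at 0, 1 and 4 hours. Protocol 1.2.4.1 says that steady state is usually reached by Day 8, so Day 10 and Day 15 also address steady state. Later ECGs come from selected patients: those given a second induction, those entering consolidation, or those still on treatment. QTc-driven dose changes (protocol Table 10) also alter later exposure. From azacitidine Cycle 4, and in cycles of glasdegib/placebo after chemotherapy, only the 1-hour ECG remains.

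**5. Baseline.** A contrast in change from baseline needs one baseline, and there are three statements:

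- Protocol 9.5.4.1: the ECG from before the first dosing day.
- SAP 3.4: the average of the pre-dose measurements on the baseline day.
- SAP 3.5: every assessment other than an adverse event on the first-dose day counts as baseline, with a pointer to SAP 3.4.

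Taken literally, the third would class the Day 1 ECGs at 1 and 4 hours as baseline.

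**The case against.** The strongest reply is that the objectives choose their verbs with care: compare for fatigue, event-free survival and patient-reported outcomes, estimate for duration of response, and characterize for PK and QTc. By-arm description is one way to characterize, it follows the rule for all safety data, and no QTc hypothesis or margin is stated. This stands as far as it goes. It argues for a descriptive contrast rather than a test. It does not remove the fact that the thing to be characterized is a treatment effect.

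Several stronger readings are tempting, and the documents do not support them:

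- A reader might infer that a drug effect could not be separated from drift or bounded at all. In fact the placebo arm is tabulated beside glasdegib with n, mean and SD, so shared drift would be visible and an unadjusted difference with an interval can be derived. What is missing is a prespecified estimate, model and printed interval.
- A reader might infer that the plan holds nothing but changes from baseline. It also has absolute means, outlier categories and shift tables, although all are per arm.
- A reader might infer that no contrast exists anywhere. There are redacted blocks in SAP 6.3, after 6.3.4 and after 6.6.8, so only the readable ECG text can be judged.
- A reader might infer that the trial fails to test against 20 msec. Protocol 1.2.4.1 gives that as the criterion of a separate thorough-QT study in healthy participants, and nothing adopts it here.

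**Conclusion.** The point holds as a gap in the readable analysis text. The objective is a treatment effect, the randomised time-matched placebo ECGs are scheduled, and protocol 9.5.4.1 and SAP 6.6.5 stop at per-arm summaries. The per-arm 90% intervals are not intervals for the effect, since they include any drift.

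From ECGs already planned, the difference would have a 90% half-width per time point of about 2.5–4.9 msec in the intensive study and 2.8–5.5 msec in the non-intensive study. This rests on an assumed SD of 15–25 msec and 70–100% attendance. At 50% attendance the upper ends become 5.8 and 6.5 msec. The finding itself does not depend on these figures.

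The primary endpoint and error control are not affected. It would go too far to conclude that exposure-response modelling must become mandatory: it can stay optional, because the randomised difference answers the objective directly.

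**What to change.** Add to SAP 6.6.5, for each study separately:

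- The glasdegib-minus-placebo difference in change from baseline in QTcF with a two-sided 90% interval. A repeated-measures model with treatment, time point, treatment-by-time point and baseline QTcF would serve. State that it is descriptive and uses no alpha.
- Emphasis on Induction 1 Day 1 and Day 10 (intensive) and Cycle 1 Day 1 and Day 15 (non-intensive), with later time points labelled as selected subsets.
- A definition of the baseline-adjusted mean.
- One ECG baseline rule that reconciles protocol 9.5.4.1 with SAP 3.4 and 3.5, so that Day 1 post-dose ECGs are not treated as baseline.

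If 20 msec is mentioned, cite it only as context from the thorough-QT study. The cost is SAP wording, alignment of the baseline sentence across the documents, and a few tables per study. No new ECGs, samples or visits are needed.

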#### **6.6.6. Physical Examination**

Physical examination findings will only be listed.

#### **6.6.7. Left Ventricular Ejection Fraction (LVEF)**

LVEF% will be summarized using simple descriptive statistics (mean, SD, median, Q1, Q3, minimum, and maximum) of actual values and changes from baseline for each nominal visit over time. In addition, a shift table will be provided for baseline versus worst on-treatment LVEF% per NCI CTCAE version 4.03.

A patient will be included in the categories above if any post-baseline assessment (including unscheduled assessments) meet the criteria; however only post-baseline assessments which use the same method of assessment (ECHO or MUGA) as baseline will be considered.

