	≤28 days prior to study entry	Induction 1 and Induction 2					Cytarabine  1-4 Cycles (28-day cycle)				HSCT period 		28-day cycle	End of Treatment Visit  (Within 14 days after last dose)	Post Treatment Follow-Up Visits (±7 days) 	Long-Term Follow-Up Activity Log (±14 days) 			
		Day 1	Every 7 days (±2 days)	Every 28 days (±2 days)	Post first Induction	Remission Assessment	Day 1	Day 5	Day 10 (±1 days)	Day 21 (±7 days)	First day of conditioning	HSCT Day 0	> Day 0, monthly (±2 days)	Day 1 (±2 days)					
Triplicate 12-lead ECG 	X	X					X		X					X	X				
ECHO or 2-D MUGA 	X																		
ANC engraftment 														X					
Registration and Treatment																			
Glasdegib or Placebo 		Oral Once Daily Continuous Dosing. If post remission HSCT  interrupt glasdegib/placebo at least 28 days prior to HSCT; may resume following ANC engraftment.																	
Daunorubicin Dosing 		Days 1-3																	
Cytarabine Dosing 		Days 1-7					Days 1,3 and 5												
Drug Compliance 		Continuous					Continuous						Continuous						
Disease Assessments																			
Bone Marrow Aspirate/Biopsy 	X-See 				X-See 	X-See 				X-See 				X-See 		X-See 			
Bone marrow genetics 	X				X-See 	X-See 				X-See 				X-See 		X-See 			
Response Assessment 						X				X-See 				X-See 		X-See 			

Protocol Activity	Screening	Induction					Consolidation Cytarabine and/or post remission HSC 							Following Consolidation(s)  : up to 2 years post randomization	Post Treatment		
	≤28 days prior to study entry	Induction 1 and Induction 2					Cytarabine  1-4 Cycles (28-day cycle)				HSC  period			28-day cycle			

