12. **Echocardiogram (ECHO) or Multigated Acquisition Scan (MUGA):** Should be repeated before Induction 2 if signs of cardiac toxicity are observed and as clinically indicated thereafter. See [Section 7.1.1](#).
13. **Subject Registration:** Subject registration and assignment of treatment will be obtained from the centralized Interactive Response Technology (IRT).
14. **Glasdegib or Placebo Dosing:** Treatment will be administered in 28-day cycles. Glasdegib or placebo will be administered orally once daily, continuously, preferably in the morning at approximately the same time each day. Where possible, glasdegib will be administered together with daunorubicin IV injection during induction. Patients may continue on glasdegib treatment for up to a maximum of 2 years, as long as they demonstrate clinical benefit and do not have CR MRD-negative disease post consolidation/HSCT as confirmed at 2 consecutive time points.
15. **Daunorubicin Dosing (Induction Only):** Daunorubicin will be given at a dose of 60 mg/m^2 daily as an IV in combination with cytarabine and glasdegib or placebo, on Days 1-3. Induction chemotherapy may be repeated for one additional induction if an unsatisfactory clinical response is observed and there are no signs of cardiac toxicity. If a second induction is needed, Investigators may choose either daunorubicin 60 mg/m^2 IV on Days 1-2 or daunorubicin 60 mg/m^2 IV on Days 1-3 with cytarabine and glasdegib or placebo. If clinical signs of cardiac dysfunction are observed, a repeat MUGA/ECHO should be performed, and must demonstrate a LVEF ≥45% to receive a second course of induction chemotherapy. If a second induction therapy is required, dose must be recalculated if the weight changes by >10%.

16. **Cytarabine Dosing:** Separate cytarabine dosing and schedules will be used for Induction and Consolidation and administered using local package inserts (or SPC) or Investigational Product Manual. Alternative single-agent cytarabine consolidation schedules may be used per local prescribing information.

**Induction:** Cytarabine will be administered (in parallel to daunorubicin) at a dose of 100 mg/m^2 daily by continuous IV infusion for 7 days on Days 1-7 of induction 1. For the second induction therapy, Investigators may choose either cytarabine 100 mg/m^2 IV on Days 1-5 or on Days 1-7. Dose must be recalculated if the weight changes by >10%.

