#### **7.1.1. Cardiac Testing (MUGA/ECHO)**

For subjects to be enrolled in the Intensive Study, an ECHO or MUGA scan is required at screening. If the LVEF is  $\geq 50\%$ , the subject may proceed to their first induction therapy. If the LVEF is  $< 50\%$ , the subject may not be included in the Intensive Chemotherapy Study, per [Section 4.2](#) and may be eligible for the treatment in the Non-intensive Chemotherapy Study.

If a second cycle of induction chemotherapy is indicated, a second MUGA or ECHO is required prior to initiating the second cycle if clinically indicated (eg, subject exhibiting signs of cardiac failure). If the second MUGA or ECHO demonstrates a LVEF  $< 45\%$ , the subject is not eligible to receive additional induction chemotherapy and will be removed from the trial.

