#### **5.2.6. Unscheduled Assessments**

Unless otherwise specified, unscheduled assessments will not be displayed in summary tables by nominal visit/timepoint. Unscheduled assessments will be used when deriving baseline and worst case on-treatment for safety and PRO analyses (except where noted for baseline ECGs). Additionally, unscheduled disease assessments will be used for efficacy analyses (eg, defining date of relapse/censoring, CRi or better, date of last contact).

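### The SAP's LVEF section plans by-visit changes that the protocol does not schedule, and its same-method rule leaves a low LVEF measured by the other permitted method out of the LVEF summary

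*SAP*

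**What the plan says.** SAP 6.6.7 has three parts. It plans descriptive statistics "of actual values and changes from baseline for each nominal visit over time". It then states that "a shift table will be provided for baseline versus worst on-treatment LVEF% per NCI CTCAE version 4.03". A closing paragraph sets the inclusion rule: "A patient will be included in the categories above if any post-baseline assessment (including unscheduled assessments) meet the criteria". A proviso in the same paragraph then narrows this to scans that repeat the screening technique: "however only post-baseline assessments which use the same method of assessment (ECHO or MUGA) as baseline will be considered".

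SAP 5.2.6 sets the general rule that, unless otherwise specified, "unscheduled assessments will not be displayed in summary tables by nominal visit/timepoint". The same section uses unscheduled values when deriving the worst on-treatment value for safety.

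In the protocol, the row "ECHO or 2-D MUGA" of Table 1 (intensive study) has a single mark, at screening. Footnote 12 says of later scans: "Should be repeated before Induction 2 if signs of cardiac toxicity are observed and as clinically indicated thereafter". Section 7.1.1 says that "a second MUGA or ECHO is required prior to initiating the second cycle if clinically indicated", and neither place requires the baseline method to be repeated. Section 7.1.1 bars further induction chemotherapy when the second scan, by either method, shows LVEF below 45%. Section 5.5.1.2 treats the same level as clinically significant cardiotoxicity. An LVEF below 50% at screening excludes a patient from the intensive study (sections 4.2 and 7.1.1).

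**The concern.** Daunorubicin is part of induction in both arms, and SAP 3.2.2 lists ECHO/MUGA among the safety endpoints. The planned LVEF output does not match how LVEF is collected, in two ways.

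First, a by-visit table of mean change presumes repeated scheduled measurements, and none is scheduled after screening. Whether a patient is rescanned is decided after randomisation by clinical signs, so it can differ between arms. A mean among those rescanned does not estimate the average change in the arm.

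Second, requiring the baseline method is sensible when two values are subtracted. It is less sensible as the only route by which a low absolute value reaches the LVEF summary, because the protocol acts on such a value whichever method produced it. A patient with a screening ECHO and a for-cause MUGA below 45% would be barred from further induction and yet be absent from the LVEF shift table.

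**Working it through.** The documents give no LVEF rate, event count or power, so there is no figure to reproduce. The check sets the passages side by side and then illustrates size on assumed rates.

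**Step 1: the by-visit table.**
- Scheduled post-baseline LVEF time points: none (protocol Table 1).
- Unscheduled values in by-visit tables: not displayed (SAP 5.2.6).
- If sites file for-cause scans under a visit, SAP 5.2.8 bases visit estimates on patients assessed at that visit, so the table describes only those rescanned.

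Either way the table is nearly empty or a for-cause sample.

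**Step 2: the shift table.**

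| Post-baseline scan | Counted in the worst-grade shift? |
|---|---|
| Same method as baseline, scheduled or not, on treatment | Yes (SAP 5.2.6 and 6.6.7) |
| Other method, any value, including below 45% | No (SAP 6.6.7) |

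**Step 3: how far a for-cause mean can sit from the arm mean.** All three inputs are assumptions: share rescanned r; mean change m in those rescanned; −2 points in everyone else.

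All-patient mean = r × m + (1 − r) × (−2). With m = −15:
- r = 5%: 0.05 × (−15) + 0.95 × (−2) = −2.65
- r = 10%: 0.10 × (−15) + 0.90 × (−2) = −3.3
- r = 20%: 0.20 × (−15) + 0.80 × (−2) = −4.6

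The table would show −15 in each case. For m from −10 to −20, the all-patient mean runs from −2.4 to −5.6.

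**Step 4: how many rescans the method rule could exclude.** N = 400 is the planned size of the intensive study. The share rescanned r and the share of rescans by the other method s are assumptions, with one rescan per patient. Excluded = N × r × s.

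| r | Rescans | s = 5% | s = 15% | s = 30% |
|---|---|---|---|---|
| 5% | 20 | 1 | 3 | 6 |
| 10% | 40 | 2 | 6 | 12 |
| 20% | 80 | 4 | 12 | 24 |

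These are rescans with any result. Those below 45% would be some unknown part of them.

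**Step 5: other gaps in the wording.** The inclusion rule refers back to categories, but the section defines none apart from the CTCAE grades of the shift table. It is therefore unclear whether the method restriction also covers the mean changes. Section 6.6.7 is also not limited to the intensive study, the only one that requires a screening scan.

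**The case against.** A reader might infer that documented cardiotoxicity is lost from the study report. The documents do not support that. Protocol 8.2.2 requires an abnormal test to be recorded as an adverse event when it comes with symptoms, leads to further testing or intervention, or leads to discontinuation. A for-cause scan below 45% would normally meet one of these. SAP 6.6.1 tabulates events by preferred term, by maximum grade and by permanent withdrawal for each drug, and SAP 6.5.2.1 tabulates reasons for discontinuation. This objection stands: the loss is from the LVEF summary. The adverse event tables do not, however, show measured LVEF, the scan method or the number rescanned.

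A reader might also infer that SAP 5.2.6 removes every for-cause scan. It does not, because same-method unscheduled scans enter the worst-grade shift table.

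A third tempting reading is that unequal rescanning would be hidden behind similar means. SAP 5.2.8 requires numbers of non-missing and missing values, so different counts would be visible. SAP 5.2.9 puts missing observations in the denominator as a separate category, and SAP 6.6 bases safety tables on the safety set by arm. Much of the needed denominator is thus already the default.

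Two limits on the facts also stand. The case report form is not available, so a pre-Induction 2 scan might be set up as a conditional visit. Footnote 12 also allows scans that are clinically indicated without signs of cardiac toxicity, so for cause is wider than symptomatic.

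Finally, a baseline-to-worst shift is itself a baseline comparison, for which a same-method rule is defensible. That justifies keeping the rule there if an any-method count of low values stands beside it.

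**Conclusion.** The point holds as a mismatch between SAP 6.6.7 and the protocol's LVEF schedule. The by-visit change table fits screening-only collection poorly, whatever the rescan rate. The exclusion of low values by the other method follows directly from the text, but its frequency cannot be known from the documents. The range of 1 to 24 excluded rescans in 400 patients rests entirely on assumed rates: 5–20% rescanned and 5–30% of rescans by the other method. The consequence is an incomplete descriptive safety summary in the intensive study. Overall survival and its tests are not touched. The change is worth making because it is cheap and alters a reported safety result.

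Separately, protocol 5.5.1.2 and 7.1.1 differ on what follows LVEF below 45% before a second induction: one stops treatment, the other takes the patient off the trial. The two must be reconciled, since the difference bears on whether such patients are followed.

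**What to change.** Amend SAP 6.6.7, for the intensive safety set:

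1. Drop the by-visit change table, or relabel it as for-cause data and give the number rescanned per arm.
2. Apply the same-method restriction to change-from-baseline values only.
3. Add, per arm over all treated patients, the number and percentage with any post-baseline LVEF <50% and <45% by any method, with method switches flagged. Both cut-offs are already in the protocol.
4. Show patients not rescanned as an explicit category in the shift table, making visible what SAP 5.2.9 already implies.
5. Define the categories to which the inclusion rule refers.

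Reconcile protocol 5.5.1.2 and 7.1.1 on the consequence of LVEF below 45%.

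The SAP change costs revised wording and one changed table, with no new scans. The downside is some between-method variability in the pooled counts, which the flag makes visible.
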